STUDY PROTOCOL AND STATISTICAL ANALYSIS PLAN

NCT Number: *Not Yet Assigned*

Official Title: *The Role of Musical Stimulation Intensity on Postural Control in Athletes: A Virtual Reality-Based Posturography Study*

Document Type: Study Protocol and Statistical Analysis Plan

Ethics Approval: Malatya Turgut Özal University Health Sciences Scientific Research Ethics Committee

Approval Number: 2025/95

Date: 28 October 2025

Sponsor-Investigator: Asst. [name]. [name]

Affiliation: Malatya Turgut Özal University, Malatya, Türkiye

1. Background and Rationale

Postural stability depends on the integration of visual, vestibular, and somatosensory inputs for equilibrium control. Auditory stimulation, particularly music, can modulate standing posture through mechanisms such as attentional modulation and stochastic resonance, which may alter proprioceptive feedback and motor strategies. The influence of different music intensity levels on balance performance in athletes remains insufficiently studied, especially using virtual reality-based posturography. This protocol evaluates how auditory intensity modulates sensory reweighting and stability indices in sport-trained individuals.

2. Objectives

Primary Objective

To investigate the effects of different musical intensity levels (low, medium, high) on postural control in athletes using VR-based posturography.

Secondary Objective

To explore whether individual noise sensitivity moderates balance performance during auditory stimulation.

3. Study Design

This experimental, cross-sectional study used a randomized crossover design. Each participant completed balance assessments under three musical intensity conditions (low ≈ 55 dB, medium ≈ 70 dB, high ≈ 85 dB). Conditions were presented in randomized order, and a ≥ 60 -second washout period was provided between trials to minimize carryover effects.

4. Participants

Inclusion Criteria

- Age 18–30 years
- Active athletic training ≥ 5 years
- Normal hearing thresholds (≤ 20 dB HL)
- No vestibular, neurological, orthopedic, or psychiatric disorders
- Written informed consent

Exclusion Criteria

- Current or past vestibular disorder or vertigo
- Intolerance to auditory stimulation
- Ototoxic drug use in the last 3 months
- Abnormal tympanometry

5. Intervention Description

Auditory stimulation consisted of *Mozart's Jupiter Symphony*, delivered via standardized VR-integrated headphones (Balance VR system). All participants listened to the same musical excerpt at three intensity levels. Balance evaluations were conducted using VR-based CTSIB and Limits of Stability modules.

6. Outcome Measures

Primary Outcomes

- CTSIB composite equilibrium score
- Sensory component scores: somatosensory, visual, vestibular, and visual preference

Secondary Outcomes

- LOS metrics: reaction time, endpoint excursion, maximum excursion, mean velocity, and directional control
- Noise sensitivity measured using the Weinstein Noise Sensitivity Scale (Turkish validated version)

7. Statistical Analysis Plan

Normality was assessed using the Shapiro–Wilk test. The effects of auditory intensity and sport type were analyzed using repeated-measures ANOVA and linear mixed models. Bonferroni correction was applied for post-hoc pairwise comparisons. Pearson correlations were performed to examine the association between noise sensitivity and postural outcomes. Partial eta-squared (η^2) was used to estimate effect size. Significance level: **p < 0.05** (two-tailed).

8. Ethics and Data Handling

The study was approved by the Malatya Turgut Özal University Health Sciences Scientific Research Ethics Committee (Approval No: 2025/95) and adhered to the Declaration of Helsinki. All participants signed written informed consent. Data are anonymized and securely stored. Individual participant data will **not** be publicly shared due to institutional data protection regulations; only aggregated results may be reported.

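### Sensory reweighting is a stated aim and the sensory component scores are primary, but Section 7 specifies no test of whether the intensity effect differs between components.

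*Combined protocol and SAP*

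**What the plan says.** Section 1 (Background and Rationale) gives two things to be evaluated, reweighting and stability: "This protocol evaluates how auditory intensity modulates sensory reweighting and stability indices in sport-trained individuals". The formal primary objective in Section 2 is broader and does not mention reweighting: "To investigate the effects of different musical intensity levels (low, medium, high) on postural control in athletes using VR-based posturography". The secondary objective concerns noise sensitivity.

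Section 6 lists as primary outcomes the CTSIB composite and "Sensory component scores: somatosensory, visual, vestibular, and visual preference", which makes five primary scores.

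Section 7 describes the main analysis in one sentence: "The effects of auditory intensity and sport type were analyzed using repeated-measures ANOVA and linear mixed models". The only multiplicity statement is "Bonferroni correction was applied for post-hoc pairwise comparisons", and the significance level is 0.05, two-tailed. The section contains no sensory-component factor, no intensity-by-component interaction and no joint test of the component scores. It also gives no rule for when a difference between components counts as reweighting.

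**The concern.** Reweighting means that reliance on one sensory input changes relative to the others. In terms of the endpoints, the effect of intensity on one component score must differ from its effect on another. Testing the vestibular score and the visual score separately at 5% does not address that. A significant result on one and a non-significant result on the other is compatible with identical true effects.

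At stake is whether the primary component scores can support the reweighting part of the Background aim. If loudness simply degrades balance across the board, separate tests can still produce a pattern that looks selective, and the plan has nothing that would distinguish the two situations.

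This is not the false-positive question across five primary scores. Adjusting alpha over the scores would leave the difference between components untested.

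**Working it through.** **Inputs.** From the document: three intensity levels in a crossover (Section 3), the component scores (Section 6), and two-sided 5% tests (Section 7). The document states no sample size, power, effect size, SD or correlation, so there is no planned figure to reproduce. Power per score and correlation between test statistics below are assumptions, shown over a range.

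**Step 1: chance of a mixed pattern under a uniform effect, three scores.** Let the somatosensory, visual and vestibular scores have the same true effect and the same power *p*. If the tests are independent, the chance that at least one but not all three are significant is 1 − p³ − (1 − p)³.

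- p = 0.5: 1 − 0.125 − 0.125 = 0.75.
- p = 0.2 or 0.8: 1 − 0.008 − 0.512 = 0.48.

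For equally correlated normal test statistics at 50% power (ignoring the negligible opposite tail), the chance is 3/4 − (3/2π)·arcsin ρ.

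- ρ = 0.5: 0.75 − 0.25 = 0.50.
- ρ = 0.7: 0.75 − 0.37 = 0.38.
- ρ = 0.9: 0.75 − 0.535 = 0.215, about 22%.

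The correlated values at 20% and 80% power come from simulation (400,000 draws).

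| Correlation | 20% or 80% power | 50% power |
|---|---|---|
| 0 | 48% | 75% |
| 0.5 | 34% | 50% |
| 0.7 | 26% | 38% |
| 0.9 | 15% | 22% |

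**Step 2: all four listed component scores.** With visual preference included and independent tests, 50% power gives 1 − 0.5⁴ − 0.5⁴ = 0.875. A full simulation used three intensities, four scores, an identical linear effect on each, and a separate repeated-measures ANOVA per score. It covered assumed n of 20 to 60, correlations of 0 to 0.6, and a high-minus-low effect of 0.3 or 0.5 residual SD. A mixed pattern appeared in 28% to 88% of trials. A multivariate (Hotelling) test of the (3 − 1)(4 − 1) = 6 interaction contrasts on the same data rejected in 4.6% to 5.5%, as a 5% test should when there is no reweighting.

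**Step 3: which interaction model keeps its 5% level.** The remedy needs care. This simulation used three scores, a uniform effect and an assumed n of 30. A mixed model with participant as the only random effect rejected about 5% of the time when there was no further participant-level variance. It rejected about 0.3% of the time when participant-by-component variance equalled the residual variance, and between 0.02% and 1.5% across the sizes and combinations of extra variance tried. Adding participant-by-component and participant-by-intensity terms restored about 5%. The simpler model errs conservatively: it does not create false reweighting claims, but it would lose real ones.

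**The case against.** The strongest case for the plan is that reweighting is not its formal question. The term appears once, in the Background, beside stability indices. The title and the primary objective concern postural control, and an intensity effect on the composite and component scores answers that directly. This stands, and a reader who infers that reweighting is the trial's primary question goes further than the text.

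Second, Section 7 does not say that each score is tested separately. The mixed model is unspecified, so a component term cannot be excluded. This also stands: separate testing is an inference from the two named effects. It does not remove the gap, because the test that the aim requires is still not stated.

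Third, a reader might infer that the investigators will report a mixed pattern as reweighting, or that 75% is the rate of wrong conclusions. The document contains no interpretation rule and no such conclusion. The percentages are chances of a mixed significance pattern, which creates the risk of a misreading. They are not error rates of a planned claim.

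Fourth, the meaning of an equal effect depends on scale, and the document does not say how the component scores are computed. Scores already normalised to a reference condition are relative measures, and a proportional loss may partly cancel in them. Standardising also changes the hypothesis, since equal raw effects with unequal SDs become unequal standardised effects. This limits any numerical reading and has to be settled in the fix. It does not make significance in one score and not another into a test of a difference.

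**Conclusion.** The point holds as a gap between one stated aim and the specified analysis. As written, Section 7 gives no basis for concluding that intensity shifts the balance between senses. The tests of intensity on each score, and the answer to the formal primary objective, are not undermined by it.

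The size is material but rests wholly on assumptions. With equal true effects on three scores analysed one by one, a mixed pattern arises in about 15% to 75% of trials over the range in the table. The low end needs very highly correlated scores (0.9), and even there the chance is not negligible. Very high or very low power would also reduce it. The change should be made, but it matters only if a reweighting conclusion is to be drawn.

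**What to change.** In Section 7, add one intensity-by-component test on the somatosensory, visual and vestibular scores. Either of these would serve:

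- a linear mixed model with intensity, component and their interaction as fixed effects, and random participant, participant-by-component and participant-by-intensity terms (or an unstructured covariance, if the number of participants can support it); or
- a multivariate test of the (3 − 1)(3 − 1) = 4 interaction contrasts.

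In the same place, state how the component scores are computed and on what common scale they are compared, and analyse visual preference separately. State that reweighting is concluded only if the interaction is significant, followed by contrasts of the intensity effect between components. Otherwise report the component results individually with no reweighting claim. The plan is written in the past tense, so if the data have already been examined, the test should be labelled post hoc.

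The cheaper alternative is to remove sensory reweighting from the aim in Section 1 and describe the component scores one by one.

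Cost: one extra model on the same measurements and a few lines of text. The interaction test has less power than the single-score tests, so a reweighting claim becomes harder to make.

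### Section 7 states no period term for a crossover with three tests per athlete, so shared practice or fatigue drift may be left in the error of the primary intensity comparison

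*Combined protocol and SAP*

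**What the plan says.** Section 3 sets out the design: "This experimental, cross-sectional study used a randomized crossover design". It continues: "Each participant completed balance assessments under three musical intensity conditions". On order and spacing it says: "Conditions were presented in randomized order, and a ≥ 60 -second washout period was provided between trials to minimize carryover effects". It does not say whether the possible orders were balanced across athletes or each athlete's order was simply drawn at random.

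Section 5 adds that the music did not change between tests: "All participants listened to the same musical excerpt at three intensity levels".

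The only description of the model is in Section 7: "The effects of auditory intensity and sport type were analyzed using repeated-measures ANOVA and linear mixed models". It lists no period, order or sequence term, and no random effects. The effect-size measure is partial eta-squared, which "was used to estimate effect size".

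**The concern.** Repeating the same balance tests to the same excerpt, with a minimum gap of about a minute, leaves room for athletes to improve with practice or tire. The washout is aimed at carryover from one intensity to the next. It is not presented as a control for practice or fatigue across the three tests.

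Random order stops such drift from favouring one intensity on average, but does not remove it from the data. A repeated-measures ANOVA or mixed model on intensity and sport type alone has nowhere to put it except the within-participant error.

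The comparison affected is the primary objective. A real intensity effect would be more likely to be missed, and partial eta-squared, which uses the same error term, would be too small. A reader of a null result could not tell absence of effect from unmodelled drift.

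**Working it through.** **Inputs from the documents.** Three conditions per athlete in random order (Section 3); named effects intensity and sport type (Section 7); two-sided 0.05 (Section 7). There is no stated sample size, SD, effect or power, so there is no figure of the plan's own to reproduce.

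**Assumptions.** Within-participant residual SD = 1. Test order gives three periods. Drift is linear, so the period effects are −d, 0, +d. Base case: N = 30, with a 55-versus-85 dB effect of 0.7 SD, linear over the three levels. Drift is either the same in all athletes (shared) or varies, with the SD of individual slopes equal to the mean drift d.

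**Closed form: balanced orders, shared drift.** Each athlete's centred period effects have sum of squares (−d)² + 0² + d² = 2d². With balanced orders this is orthogonal to intensity, so all 2Nd² falls into a residual with 2N − 2 degrees of freedom:

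expected residual mean square = 1 + 2Nd²/(2N − 2)

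At N = 30 the factor on d² is 60/58 = 1.034.

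| d (SD per period) | Mean square | SE inflation (square root) | Equivalent loss of athletes (1 − 1/mean square) |
|---|---|---|---|
| 0.1 | 1.010 | 0.5% | 1% |
| 0.25 | 1.065 | 3.2% | 6% |
| 0.5 | 1.259 | 12.2% | 21% |

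**Simulation: power of the 2-df F test for intensity, N = 30, without / with period.** There were 10,000 replicates per cell (Monte Carlo SE about 0.5 point), with least squares on participant-centred data. In one simulated dataset a random-intercept REML mixed model gave the same estimate and SE.

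| d | Balanced, shared | Simple, shared | Balanced, varying | Simple, varying |
|---|---|---|---|---|
| 0 | 66.1 / 66.0% | 64.9 / 63.5% | – | – |
| 0.1 | 64.9 / 65.1% | 64.8 / 63.5% | 65.0 / 65.4% | 64.5 / 62.8% |
| 0.25 | 61.7 / 64.6% | 62.5 / 63.6% | 59.1 / 61.8% | 59.8 / 61.0% |
| 0.5 | 54.0 / 65.3% | 55.6 / 63.7% | 46.0 / 55.5% | 47.4 / 53.3% |

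A period term removes only the shared part of the drift, so power still falls when drift varies between athletes.

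**Other sample sizes.** At N = 18 (effect 0.9 SD) and N = 60 (effect 0.5 SD) the gain from period runs from −0.7 to 2.8 points at d = 0.25 and from 4.6 to 12.2 points at d = 0.5.

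**Type I error, N = 30.** Without period it never rises materially above 0.05. With balanced orders and shared drift it falls to 0.040 at d = 0.25 and 0.024 at d = 0.5, so the test is conservative. With simple randomisation it stays at 0.046 to 0.053. With period it is 0.047 to 0.052 throughout.

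**Where the loss arises: separate check at N = 24, d = 0.5, shared drift.**

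| Orders | Empirical SD of 85-versus-55 dB estimate, without / with | Mean SE, without / with |
|---|---|---|
| Simple | 0.324 / 0.295 | 0.321 / 0.293 |
| Balanced | 0.292 / 0.292 | 0.322 / 0.287 |

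Under simple randomisation the estimate really is more variable. Under balanced orders the estimate is the same in both models and only its reported SE is too large. Bias was about zero in every case.

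**Mean partial eta-squared, N = 30, shared drift, without / with period.** Balanced: 0.130 / 0.141 at d = 0.25 and 0.113 / 0.142 at d = 0.5. Simple: 0.131 / 0.137 and 0.116 / 0.136.

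**The case against.** The strongest reply is that Section 7 names the effects of interest and is not a full model specification. It omits random effects too, and a period term may have been fitted without being written down. That stands, and it is why the point is conditional. Even so, this is the plan's only statement of the model, and a repeated-measures ANOVA run on it as written leaves drift in the error.

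Second, nothing is invalidated. That also stands: a positive intensity result is not undermined, and with balanced orders the test without period errs on the safe side.

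Third, the size is assumed. At 0.1 SD per test under simple randomisation the period term lowers power slightly, and the gain becomes material only near 0.5 SD per test, a shift of 1 SD from first to third test that no document supports. The gain also depends on the effect. At N = 30 with a 1.0 SD effect and shared drift of 0.5 SD it falls to about 5 points (88.8% to 93.5% balanced; 86.9% to 92.3% simple). These limits are accepted. They narrow the likely benefit but do not make the omission the better choice, because the cost without drift is small.

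Fourth, the text is in the past tense, so the study may be finished. That affects how a change is labelled, not whether it is useful.

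**Conclusion.** The concern holds as a conditional loss of power on the primary comparison, not as bias or false-positive risk. If the models contain only intensity and sport type, the base case (30 athletes, 0.7 SD effect) gives up nothing at a drift of 0.1 SD per test and 1 to 3 points of power at 0.25 SD. At 0.5 SD it gives up about 8 to 11 points if drift is shared and 6 to 10 if it varies between athletes. Every one of these figures rests on an assumed sample size, effect and drift; the documents supply none of them. The change should be made because it is standard for this design and cheap. Confidence is medium, since the true drift and the model actually fitted are unknown.

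**What to change.** In Section 7, add period (first, second or third test) as a fixed effect, with a random participant effect, to the linear mixed model already named, keeping its other planned terms. Report the period estimate with its confidence interval. In Section 3, state how the orders were generated and whether they were balanced. If results have already been seen, keep the analysis as written and present the period-adjusted model beside it, labelled as a later addition.

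The cost is a sentence or two of wording and one model term using two degrees of freedom. With no drift that term costs 0.1 (balanced) to 1.3 (simple) points of power at N = 30, and at most 2.9 points at N = 18. It requires that each athlete's test order was recorded, which the document does not state.

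### Does naming both repeated-measures ANOVA and mixed models, with no deciding test or sphericity correction, make the intensity test unsound?

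*Combined protocol and SAP*

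**What the plan says.** The primary objective in section 2 is "To investigate the effects of different musical intensity levels (low, medium, high) on postural control in athletes using VR-based posturography". Section 3 describes a crossover with the three intensities given in random order, and says "Each participant completed balance assessments under three musical intensity conditions". Section 5 adds that "All participants listened to the same musical excerpt at three intensity levels".

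Section 7 gives the analysis in one sentence: "The effects of auditory intensity and sport type were analyzed using repeated-measures ANOVA and linear mixed models". The only assumption check is "Normality was assessed using the Shapiro–Wilk test", and the only adjustment is "Bonferroni correction was applied for post-hoc pairwise comparisons". Significance is two-sided at 0.05.

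The document does not say which method decides, how sphericity is handled, what covariance the mixed model uses, or whether the pairwise comparisons use paired or pooled error. It gives no sample size, number of sport types or variance estimate.

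**The concern.** Two methods are named for the primary question and neither has priority. If they disagreed, the authors could report the more favourable one. Three repeated measurements per participant also mean that the univariate F test relies on equal variances of the pairwise differences (sphericity), and a Shapiro–Wilk test says nothing about that. If sphericity fails and no correction is made, the ANOVA rejects too often. Together these would put the false-positive rate for the primary objective above the stated 5%, by an amount the plan does not bound.

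**Working it through.** The plan states no design figure to reproduce beyond the 5% level. The number of levels, k = 3, comes from section 3. Everything else is assumed: N = 20 to 30, two or three equal sport groups, complete data, correlation 0.6 between conditions, no intensity effect, and one condition with variance v against 1 for the other two.

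**Step 1: how far sphericity fails.** With three levels, ε = (λ₁ + λ₂)² / [2(λ₁² + λ₂²)], with minimum 1/(3 − 1) = 0.5. For the assumed covariance:

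- λ₁ = Var[(X₁ − X₂)/√2] = (1 + 1 − 1.2)/2 = 0.4
- λ₂ = Var[(X₁ + X₂ − 2X₃)/√6] = (3.2 + 4v − 4.8√v)/6

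For v = 2, λ₂ = (3.2 + 8 − 6.788)/6 = 0.735, so ε = 1.135²/[2(0.160 + 0.541)] = 0.92.

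**Step 2: false-positive rate at nominal 5%.** Each setting used 40,000 simulated trials. The Monte Carlo standard error is √(0.05 × 0.95/40,000) = 0.11 percentage points. The mixed model is represented here by an unstructured covariance (Hotelling's T² on the within-participant contrasts).

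| v | λ₂ | ε | Uncorrected ANOVA | Claim if either test significant | Claim only if both significant |
|---|---|---|---|---|---|
| 1 | 0.400 | 1.00 | 5.0–5.2% | 6.1–6.5% | 3.5–3.9% |
| 1.5 | 0.554 | 0.975 | 5.0–5.1% | 6.3–6.6% | 3.4–3.8% |
| 2 | 0.735 | 0.92 | 5.3–5.4% | 6.8–7.0% | 3.2–3.6% |
| 3.12 | 1.200 | 0.80 | 5.9–6.1% | 7.7–8.1% | 3.0–3.2% |
| 8.675 | 3.960 | 0.60 | 7.5% | 9.6–9.8% | 2.7–2.9% |

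A single test is well behaved in every row: Greenhouse–Geisser 4.3–5.0%, Huynh–Feldt 4.7–5.2%, unstructured 4.8–5.2%. A repeat run with separate code agreed to within about 0.4 percentage points; its highest uncorrected value at v = 2 was 5.6%. At the theoretical floor, ε = 0.5, the uncorrected test reaches 8.4–9.0% for N from 15 to 100, simulated without sport groups.

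**Step 3: does the design produce non-sphericity?** Serial correlation is a common cause. Take correlation 0.7 between adjacent trials and 0.7² = 0.49 between the first and third. In a fixed order, ε = 0.875. If all six orders are equally likely, each pair of intensities has average correlation (0.7 + 0.7 + 0.49)/3 = 0.63. The covariance indexed by intensity is then compound symmetric and ε = 1. In simulation, the uncorrected ANOVA rejected in 5.4–5.8% of trials under fixed order and 4.8–5.0% under random order. Only variances or correlations that differ by intensity remain as a cause, and the document points to none.

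**Step 4: must the two methods conflict?** On one complete simulated data set of 30 participants, the ANOVA gave F = 1.432 on 2 and 2 × 29 = 58 degrees of freedom. A random-intercept mixed model gave a Wald χ² of 2.865, and 2.865/2 = 1.432. The statistics are the same; the p-values (0.247 and 0.239) differ only because one uses an F and the other a χ² reference.

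**Step 5: pairwise comparisons.** The chance of any false claim after Bonferroni is 3.7–4.6% with paired error throughout. With pooled error it is 4.2–4.7% up to v = 2, then 5.1–5.3% and 6.0–6.1%.

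**The case for a change.** The strongest case for a change does not need non-sphericity. If the mixed model has an unstructured covariance, it is a different test from the ANOVA. Claiming on whichever is significant then gives 6.1–6.5% even at ε = 1. With a real linear effect (low–high difference of 0.5 to 0.7 paired-difference SDs, two sport groups, sphericity holding), the two tests give opposite verdicts in 9–11% of trials at N = 20 and 3–8% at N = 30. A random-intercept model that matches the ANOVA is no safeguard either, since it relies on the same sphericity. One sentence would settle the matter, and because individual data will not be shared, outside readers could not rerun the alternative.

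The arithmetic stands, and so does the observation that the plan sets no order. But the conflict figures depend on a covariance structure and a claim rule that appear nowhere in the plan. Requiring both tests, which is equally consistent with the text, gives 2.7–3.9%, so even the direction of any error is not established. The inflation of the ANOVA itself needs both an uncorrected analysis, which the plan does not state, and a variance ratio for which the document gives no evidence either way.

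**Conclusion.** No change follows. Section 7 leaves out detail that a competent analyst fills in routinely: an epsilon correction for the ANOVA, or a mixed model with a covariance that does not assume sphericity. Each of these, used alone, held its error between 4.3% and 5.2% in the assumed settings of Step 2.

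The choice among them matters little. For a low–high difference of 0.7 paired-difference SDs at N = 20 with sphericity holding, power is 77% uncorrected, 75% with Greenhouse–Geisser, 76% with Huynh–Feldt and 72% unstructured. At N = 30 the figures are 93%, 92%, 93% and 91%. More than one primary model would be acceptable, and no stated rule has been shown to give a wrong result. Section 7 is also in the past tense; if results have been seen, an order set now would not count as prespecified.

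This rests on complete data, on all orders being equally likely, and on one intensity not having several times the variance of the others. The document gives neither the sample size nor the covariance. Missing conditions and period effects were not simulated, and multiplicity across the primary outcomes is a separate question not judged here.

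### Five unranked primary scores are each tested at p < 0.05 with no rule across them; if any one can carry the claim, the false-positive chance is about 9% to 23%, depending on their correlation

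*Combined protocol and SAP*

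**What the plan says.** Section 6 (Outcome Measures) puts two entries under the primary heading: "CTSIB composite equilibrium score" and "Sensory component scores: somatosensory, visual, vestibular, and visual preference". The second entry holds four scores, so there are five primary outcomes. None is called key, and no order of testing is given.

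The primary objective in section 2 is broad: "To investigate the effects of different musical intensity levels (low, medium, high) on postural control in athletes using VR-based posturography". It names no deciding score.

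Section 7 (Statistical Analysis Plan) gives the test, "The effects of auditory intensity and sport type were analyzed using repeated-measures ANOVA and linear mixed models", and one threshold, "Significance level: p < 0.05 (two-tailed"). The only adjustment for multiple testing is "Bonferroni correction was applied for post-hoc pairwise comparisons", which in ordinary usage covers the contrasts between intensity levels within an outcome. Neither section contains a hierarchy, an alpha split, a global test, or a statement of how many primary scores must be significant.

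**The concern.** The plan yields five primary omnibus tests of intensity, each at 0.05. The Bonferroni step works inside an outcome, between low, medium and high, and does not reach across outcomes. The error rate of the primary conclusion therefore depends on a success rule that the plan does not state.

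A broad objective served by five unranked scores leaves room, once results are known, to present whichever score is significant as the effect on postural control. Under that reading the 5% level is not the error rate of the conclusion. Under other readings it is, or it is an upper limit, and a reader of the plan cannot tell which applies.

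**Working it through.** The plan gives no family-wise error rate, power or sample size, so there is no figure of its own to reproduce.

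**Inputs from the documents**
- Five primary scores: 1 composite + 4 sensory components (section 6).
- Level 0.05, two-tailed (section 7).
- Three conditions per participant (section 3: "Each participant completed balance assessments under three musical intensity conditions"), hence an omnibus test with 2 numerator degrees of freedom and three pairs per score.

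**Assumptions, because the documents are silent**
- N = 30, giving F(2, 58) with 58 = 2 × 29; N = 20 and 60 as checks.
- One common correlation between the five scores, varied from 0 to 1.
- Normal, spherical errors and complete data.
- One intensity test per score. Sport type, and the use of two kinds of model, could add tests; they are not counted.

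**Step 1: independent scores, all five nulls true, any rejection counted**

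1 − (1 − 0.05)^5 = 1 − 0.7738 = 0.2262, or 22.6%.

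**Step 2: correlated scores**

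Simulated repeated-measures ANOVA under the null, 40,000 runs per setting, standard error at most 0.0021:

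| Assumed correlation | Any omnibus p < 0.05 | Omnibus p < 0.05 plus a Bonferroni-significant pair in the same score |
|---|---|---|
| 0 | 22.8% | 17.1% |
| 0.3 | 21.3% | 16.0% |
| 0.5 | 18.5% | 14.1% |
| 0.7 | 15.3% | 11.8% |
| 0.9 | 10.7% | 8.1% |
| 0.95 | 8.8% | 6.7% |
| 1 | 5.0% | 3.6% |

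A separate simulation at correlation 0.5 gave 18.7% at each of N = 20, 40 and 60, hence about 19%. Taking N = 20 or 60 in place of 30 moves the checked entries (correlation 0, 0.5 and 0.9) by about 1 point or less.

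**Step 3: other success rules**
- All five must be significant. With all nulls true, the rate is about 0% at correlation 0, 1.5% at 0.9 and 5.0% at 1. The worst case, four large real effects and one null, has a nominal rate of 5% (simulated 5.1% to 5.2%, standard error 0.18 points).
- Each score is its own separate finding. Each keeps its own 5% and there is no joint claim to inflate.

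**Step 4: Holm across the five**

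The first step is 0.05/5 = 0.01. With all nulls true, the chance of any rejection at 0.01 is 4.9% at correlation 0, falling to 1.0% at correlation 1. Holm holds the family at 5% or less under any dependence, so the unknown correlations do not matter for this guarantee.

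**Step 5: power cost**

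For a score with 80% power at 0.05, power at 0.01 is Φ(2.8016 − 2.5758) = Φ(0.2258) = 58.9% for a 1-df test, or 57.7% for the noncentral F(2, 58) with λ = 10.15. Simulated per-score power under the full Holm procedure (N = 30, correlation 0 to 0.9) is 58% with one real effect, 61% to 62% with three, and 66% to 70% with five.

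**Step 6: what Holm on the omnibus tests leaves open**

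Suppose that in every score one intensity differs strongly and the other two are equal. All five omnibus tests then pass, and each score has one truly null pair tested at 0.05/3. For independent scores the chance of at least one false pair is

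1 − (1 − 0.05/3)^5 = 1 − 0.9194 = 8.1%.

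Simulated (N = 30): about 8%, 7% and 4% at correlation 0, 0.5 and 0.9. This is one configuration, not a proven ceiling.

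**The case against.** **The any-one rule is not in the plan.** The objective is to investigate effects, no success criterion is stated, and an effect size is planned beside the p-values. This stands in part. A reader might infer that the plan has a 22.6% false-positive rate. The documents do not support that: the figure needs both the any-one reading and independent scores, and they state neither. What is certain is the missing rule; the inflation is conditional on how the results are read.

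**Independence is the least plausible case.** All five scores come from the same participants, and a composite sits beside sensory components. This stands, which is why the result is given as a range. Correlation shrinks the problem, but the any-one rate is still about 9% at 0.95 and falls to 5% only at perfect correlation.

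**The composite is listed first, so it is the real primary.** Order in a list is not a stated hierarchy, and all five scores share one heading.

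**Bonferroni on the pairs already protects.** It lowers the rate, as the last column of the table shows, but it does not act across scores.

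**The study is exploratory.** The plan calls these outcomes primary and sets a formal level; its exploratory wording is attached to the secondary objective.

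**Holm picks a rule for the sponsor.** This also stands in part. A single deciding score, or a requirement that all five be significant, would control error too, provided it was fixed before results were seen. The documents show no such rule, and section 7 is in the past tense, so choosing one now could be choosing after the fact. The fix leaves room for a rule that can be shown to predate the results.

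**Conclusion.** The concern holds in conditional form. Five unranked primary scores are tested at 0.05 each, and nothing in the plan controls error across them. If any one can carry a claim about postural control, the false-positive chance is about 9% to 23% for assumed correlations from 0.95 down to 0, or about 7% to 17% if a Bonferroni-significant pair is also required. If all five must be significant, or each is its own finding, there is no such inflation.

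The gap itself is certain from the text. Its size is not, because it rests on the simulation assumptions above and on the unstated success rule. It should be fixed, because it bears on the primary conclusion and can be settled in the analysis.

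A reader might also infer that Holm on the omnibus tests, with Bonferroni kept within each score, holds every claim at 5%. It does not: the guarantee covers the omnibus claims only.

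**What to change.** 1. Name one model, either the repeated-measures ANOVA or the linear mixed model, as the source of the five primary intensity p-values. Without this, each score could supply two candidate p-values and Holm's guarantee would not hold.
2. Apply Holm across those five omnibus tests, and report unadjusted and Holm-adjusted p-values side by side.
3. Base any overall claim of an effect on the Holm-adjusted values. The exception is a dated rule, set before results were seen, that one named score decides or that all five must be significant; in that case cite it and follow it.
4. Keep Bonferroni for pairs within a score, and interpret pairs only for scores that pass Holm. State that the 5% guarantee covers the omnibus claims only, and that pairwise error across the five scores can still reach about 8%.
5. Date the change and say whether results had been seen. If they had, label the adjustment post hoc.

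The cost is analysis and wording only, with no new data. The price is power: about 58% to 70% per score in place of 80%, depending on how many of the five effects are real.
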